### **9.2. Sample Size Considerations**

The following was performed for each of the proposed LAR primary endpoints:

[figure not shown]
- Success criteria: declare endpoint success if the posterior probability of any treatment attenuation exceeds 0.7.
- The probability of declaring a success has been computed for a range of true percent attenuations and sample sizes (n per arm equal allocation). To make the figures easier to interpret the “nuisance” parameters of the placebo response and the standard deviation have been accounted for as follows:
- Eight previous GSK BAC studies (Crossover design) have been re-analysed to obtain estimates of the average placebo response and the associated estimate of residual variability applicable to the proposed Parallel Group design.
- These estimates were combined in a random effects meta-analysis to obtain posterior distributions for the underlying parameter values (placebo average response, residual variability (for an individual subject) and a between study variance component). The future placebo response was computed as the sum of random draws from the posterior distributions of the placebo average response parameter and a normal distribution with mean zero and variance equal to the between study variance parameter. The future GSK2245035 response was derived using the simulation scenario’s true percentage attenuation. A pooled sample variance value was generated using a Chi-Square distribution with degrees of freedom appropriate to the simulation scenario and a sampled variance from the meta-analysis posterior distribution. Those numbers were entered into the standard formulae for power curves. Repeating this process 10,000 times and taking the median of the resulting power values constructs “Assurance” operational characteristics for the combination of true percent attenuation and sample size under evaluation.

- These assurance operational curves have been summarised graphically. The x-axis is a hypothetical true drug effect that is assumed to be known for experimental design purposes.
- The simulations can also be used to compute the minimum observed percentage attenuations that would result in a successful study outcome. The median (of the 10,000 simulations) have been derived for a variety of sample sizes and success criteria (probability thresholds 0.7, 0.75, 0.8, 0.85, 0.95) and displayed graphically. The y-axis is the observed effect from the study data.

[figure not shown]

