**Table 2 Input data for Sample Size Work**

GSK Internal Study ID	LAR Minimum FEV1 between 4-10h			LAR Weighted Mean FEV1 between 4-10h		
	Average Placebo Response	Degrees of Freedom	Residual Variability	Average Placebo Response	Degrees of Freedom	Residual Variability
PPD	-1.3975	33.5	0.40571	-0.9462	33.1	0.30417
	-1.0864	45.9	0.13063	-0.7093	42.3	0.11430
	-1.1238	22.9	0.30521	-0.6916	22.8	0.18820
	-0.9006	48.9	0.07344	-0.3749	47.9	0.02191
	-0.7309	85.3	0.10717	-0.4662	84.4	0.07528
	-0.9027	31.9	0.27740	-0.5502	34.0	0.20925
	-1.4484	20.4	0.40528	-0.9817	20.3	0.31342
	-0.8129	69.6	0.15866	-0.5260	71.8	0.08695

Assuming the true treatment effect of GSK2245035 is no worse than the results from the AstraZeneca study and 20 subjects complete follow up assessments the probability of meeting the success criteria for Min LAR and WM LAR are approximately 78% and 81% respectively. This is considered sufficient justification for requiring 20 completers.

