For each treatment arm the (joint) posterior predictive distribution of an individual subject's primary endpoints will be obtained (separate Variance Covariance (VCV) matrices for each treatment arm are preferred to cover the case where variability is also a function of treatment; but there may not be sufficient information in the interim dataset to estimate the required parameters, in which case a pooled VCV matrix across treatment arms would be acceptable). The predictive distributions will be used to simulate a sufficient number of future subjects to achieve the end of study sample size (planned to be 20 per arm, but may be revised upwards to a value between 21 and 30 per arm depending on the observed placebo non-LAR responder rates). Summary statistics (sample mean and sample variance covariance matrix) will be derived using each set of simulated subjects for each treatment. These summary statistics are used as informative prior distributions for the treatment parameters in models fitted to the observed interim data (with the simplifying assumption that these models exclude allergen exposure covariate(s)). If the resulting posterior probability of any attenuation exceeds 0.7 (for either endpoint) the hypothetical end of study result is a success. By repeating the process of simulating sets of future subjects (10,000 times); producing informative priors for the treatment parameters from those simulated subjects and combining with the (unchanging) observed interim dataset in a model to evaluate individual study success an expected probability of a successful outcome can be obtained if the study were allowed to continue past the interim (i.e. the number of simulated sets flagged as successful / total number of simulated sets of subjects).

The advantage of utilising posterior predictive distributions is that they also account for the uncertainty in the true values of the parameters (caused by having to estimate them using only the interim data). Note: Each simulated subject can be thought of as being generated using the average of each of the covariate values. Therefore sample statistics are used as priors for the treatment related parameters only in the subsequent modelling step. This avoids having to generate covariate values for the simulated subjects (e.g. assign them to a centre, or generate a baseline response for them).

Further details are given below:

Interim Analyses to estimate end of study success

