Step 1: Obtain posterior predictive distribution for a future subject (separate distribution for each treatment arm)

 The endpoints (transformed if necessary) will be assumed to follow a multivariate normal (MVN) distribution. Linear predictors will be derived for each subject (i.e. a vector of means for the MVN distribution). Each treatment arm will also have a separate variance covariance matrix, i.e. 
To link to observed data assume : $\begin{bmatrix} WM & Min \\ y_1 & y_2 \end{bmatrix}_i \sim MVN \left(\begin{bmatrix} WM & Min \\ \hat{y}_1 & \hat{y}_2 \end{bmatrix}_i, [\Sigma_{Pbo} \ \Sigma_{Act}] \right)$ where Σ_{Pbo} & Σ_{Act}
 
 are separate 2x2 Variance Covariance matrices for each treatment arm and $\begin{bmatrix} WM & Min \\ \hat{y}_1 & \hat{y}_2 \end{bmatrix}$ represents the linear predictor for the ith subject for the two endpoints 
The linear predictors will consist of mean vectors to capture i) the effect of treatment for each endpoint, ii) a continuous baseline for each endpoint and iii) a random centre effect for each endpoint (drawn from $Normal(0, SD_{\text{endpoint}})$ distribution).
 
 Baseline vectors will be fitted as continuous covariates (baseline values should be centered prior to inclusion in the model, centering to occur after any transformation of the individual subjects responses). Non-informative priors will be utilized for each model parameter assigned either as a normal distribution centered on 0 with large variance 1E6 or as appropriate to the parameters distribution. The prior for the variance covariance matrices Σ_{Pbo} and Σ_{Act} will be an inverse Wishart distribution. SAS PROC MCMC will be used to combine the non-informative priors with the observed interim data to obtain sufficient draws from the posterior distribution (after any thinning) such that the MCSE/SD values for parameters of interest are less than 0.01 (anticipated to be in the region of ~100,000 draws). If model convergence is poor then alternative initial parameter values should be considered. Note: A SAS coding trick may be required if the MCMC procedure does not automatically detect the conjugacy (occurs in SAS v9.3 when fitting separate variance covariance structures to treatments in a multivariate normal distribution and may occur in SAS v9.4 as well). The trick involves setting up duplicate sets of variables in the input dataset with some populated as missing values and having 2x model statements (see GSK study statistician for details if required). The randomization seed used in PROC MCMC should itself be generated with an element of randomness - but there is no need to formally document this process (e.g. using Excel function RANDBETWEEN [1,9999999] and copying the result into the SAS code) The following describes the anticipated linear predictor for a hypothetical subject from center 3 (out of 5), on active treatment with centered baseline values of -4.1 and -0.5 for BS1 (WM) and BS2 (Min) respectively (Note: although not anticipated additional covariates may be explored and added based on the observed data).

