
 • LAR: minimum <change from saline baseline> FEV₁ between 4-10 hours following allergen challenge at the three follow up visits (i.e. FUV1, FUV2 and FUV3). • LAR: weighted mean of <change from saline baseline> FEV₁ between 4-10 hours following allergen challenge at the three follow up visits (i.e. FUV1, FUV2 and FUV3). • Note: Text in <> added for clarity, since the wording in the protocol and objectives is familiar to clinical experts in the field, but may be confusing given there are also absolute FEV1 values measured at those times too. • Any transformation of a response variable is also expected to be applied to the corresponding baseline variable. Final decisions on transformations will be based on the observed data and model diagnostics • Any observations with missing model covariates (e.g. baseline) would be excluded from the model fitting process (i.e. also excluding the record from any centering of covariates) 	
Model Specification	

 • Each endpoint will be analysed separately using a Bayesian Mixed effects repeated measures model fitted within Proc MCMC in SAS using the following approach: • Assume equal variances across treatment arms and use a pooled estimate of residual 	

Exploratory Statistical Analyses: Repeated measures version LAR Primary analysis model

variability (i.e. a 3x3 Variance Covariance Matrix). Note: if the posterior predictive distributions produced to support the interim analysis suggest this assumption may be invalid then the modelling approach may be modified to estimate separate variance covariance matrices for each treatment arm.

- **Step 1:** Fit all three of the following models (report output from each model in the same listing – along with the DIC values and changes in DIC values between models). Using a combination of changes in the DIC criteria, **and expert judgment** (see Section 11.9.1), select a single model.
- R1: Intercept + Centre + Baseline*Visit + Treatment + Visit + Allergen Exposure + Treatment*Visit + Allergen Exposure*Visit + Treatment*Allergen Exposure + Treatment*Allergen Exposure*Visit
- R2: Intercept + Centre + Baseline*Visit + Treatment + Visit + Allergen Exposure + Treatment*Visit + Allergen Exposure*Visit
- R3: Intercept + Centre + Baseline*Visit + Treatment + Visit + Treatment*Visit
- See Section 11.4.2 for Baseline definitions (Screening visit 2 BAC endpoint).

Where in each of the models (R1, R2 and R3) the effects are:

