
$*$=Centre covariates prior to fitting model (do not use observations that will not contribute to the planned model when centering) and if applicable the centering is to occur after any transformations have been applied
 
Δ=If chain is not mixing (i.e. sticking at values close to zero) an additional mixture prior may be considered to act as a lower boundary constraint, or the centre term excluded from the model
				

 • Step 2 (optional): Explore adding other covariate terms to the Step 1 model (for example, but not limited to, Age, Gender, Dose per kg, Blood eosinophil levels). Use expert judgment and changes in DIC to determine final model to take to Step 3. Include any Step 2 models in the listing output and add the associated DIC / changes in DIC values to those produced in Step 1. • Step 3: For the finally selected model use appropriate combinations of the model parameters (back transforming the combination if necessary) to obtain posterior distributions for the quantities of interest described in the Model Results Presentation. Binary flag variables can be used to evaluate the probability statements, by tracking the instances of the desired event happening over each MCMC iteration and taking the mean of the flag variable as the probability. • Similar MCMC model fitting options and techniques to the Primary Statistical Analysis will be employed (see Section 7.1.2). • In addition posterior probabilities of the differences (and/or percentage attenuations) for other cut-points (which may be determined upon inspection of the data, or from developing business requirements), may also be computed. 				
<h3>Model Checking & Diagnostics</h3> 
 • Refer to Appendix 11: Model Checking and Diagnostics for Statistical Analyses. • This analysis can also be used to confirm the results of the Primary Statistical Analysis (see Section 7.1.2). Further investigation should be undertaken if results between the single timepoint Bayesian model (Primary) and Bayesian Repeated Measures model at FUV1 are inconsistent (a priori the most likely causes would be related to missing data influencing the estimates of the respective model's variance covariance parameters and/or the centre effects being a function of all three visits in the repeated measures modeling). 				

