11.11 Appendix 11: Model Checking and Diagnostics for Statistical Analyses

11.11.1 Statistical Analysis Assumptions

Endpoint(s)	
 • All which are modelled using a Bayesian framework
Analysis	
 • Bayesian (Proc MCMC)

General Considerations for Bayesian Analyses (PROC MCMC):

The following points are for guidance and illustration and do not guarantee a successful model convergence. They cannot cover all eventualities and do not remove the requirement to do what is best for the specific set of observed data being modelled.

Priors:

Unless otherwise specified the following would be the default approach to selecting prior distributions:

- Non-informative priors of the form $\text{Normal}(0, \text{Var}=1\text{E}6)$ would be assigned to each fixed effect in the proposed statistical model.
- Non-informative Inverse-gamma priors of the form $\text{IGamma}(0.001, 0.001)$ would be assigned to stand-alone variance parameters that are not expected to take values near zero (e.g. for the residual variance rather than a random effect variance component)
- For stand-alone variance parameters that may take values close to zero a non-informative prior of the form $\text{Uniform}(0, \text{XXX})$ may be assigned for the SD
- For repeated measures models non-informative Inverse-Wishart priors will be assigned for the Variance Covariance matrix (VCV). They would use degrees of freedom equal to the dimension of the VCV matrix and an Identity matrix (of the same dimension).
- If there are issues with those variance parameters then the Identity matrix may be replaced with a diagonal matrix that uses best guesses for the residual variance at each repeated measure time point (or the residual estimates from fitting simple models)
- It is good practice to ensure that each prior distribution is visualised to ensure it appears sensible and allows clinically plausible response values, whilst not allowing impossible values to be drawn with high probability and that if it is intended to be non-informative it is doing so over the region of the likelihood function.

Note: There is no requirement to formally report these visualisation outputs.

Initial Values:

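### The inverse-Wishart prior with identity scale is not non-informative for FEV1 in litres; it modestly widens the LAR repeated-measures intervals, and its settings at interim are not stated

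*SAP*

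**What the plan says.** SAP Section 11.11.1 (Priors) states: "For repeated measures models non-informative Inverse-Wishart priors will be assigned for the Variance Covariance matrix (VCV". The next sentence fixes the settings: "They would use degrees of freedom equal to the dimension of the VCV matrix and an Identity matrix (of the same dimension". The identity may be replaced by a diagonal matrix of best-guess or simple-model residual variances, but only if the variance parameters give trouble. The same list recommends, without formal reporting, checking that a prior meant to be non-informative really is so where the likelihood lies.

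The rule reaches LAR through the repeated-measures model in SAP Section 8.1.2, which pools residual "variability (i.e. a 3x3 Variance Covariance Matrix" over the arms. That section adds: "This analysis can also be used to confirm the results of the Primary Statistical Analysis". The EAR repeated-measures model follows the same specification.

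At the interim (SAP Section 3.1, Step 1), the prior for each arm's 2x2 matrix of the two LAR endpoints "will be an inverse Wishart distribution", with no degrees of freedom or scale. Separate matrices are preferred, but "a pooled VCV matrix across treatment arms would be acceptable" if data are thin.

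**The concern.** A scale matrix has units. The identity means 1 L² on each diagonal. For log2 biomarkers with variances near 1 that may be harmless; for FEV1 changes with variances well below 1 L² it inflates the variance. The prior's zero off-diagonals also dilute the covariances, so correlations between visits, or between the two LAR endpoints, shrink.

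Two uses are at stake. The repeated-measures model cross-checks the primary FUV1 result and is the planned model for the week 4 and week 12 treatment effects. Section 8.1.2 names missing data and centre effects as the likeliest causes of disagreement with the primary model, so a difference caused by the prior could be misattributed. At interim, the covariance matrix generates the future subjects from whom end-of-study success is predicted.

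The listed diagnostics (Monte Carlo error ratio, autocorrelation, trace plots) assess convergence. A chain with an inflated variance converges cleanly, so they would not reveal the problem.

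**Working it through.** **Inputs.** Protocol Table 2, residual variances from eight studies:

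| Endpoint | Range | Simple mean | Df-weighted mean |
|---|---|---|---|
| Minimum LAR | 0.07344-0.40571 | 0.233 | 0.188 |
| Weighted-mean (WM) LAR | 0.02191-0.31342 | 0.164 | 0.130 |

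Mean placebo responses are -1.0504 L and -0.6558 L. There are 20 completers per arm, about 14 per arm at an interim of 28, and the protocol rule is to "declare endpoint success if the posterior probability of any treatment attenuation exceeds 0.7".

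**1. The plan's own figure.** Protocol Section 9.2.1 gives about 78% and 81% probability of success. The assumed effects are 0.18 × 1.0504 = 0.189 L and 0.27 × 0.6558 = 0.177 L. A one-sided two-sample calculation at 0.30 with the simple-mean variances gives 76% and 80%. Df-weighted variances give 80.3% and 84.8%, a poorer match. Both sets are carried below.

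**2. The prior.** With df equal to the dimension and an identity scale, each variance has marginal prior IG(1/2, 1/2). Its median is 2.2 L², with 12% of its mass below 0.41 and 2.5% below 0.20. Every Table 2 value lies in this lower tail.

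**3. Final repeated-measures model.** Residual df r = 40 - 3 = 37 (intercept, treatment and baseline slope per visit; centre ignored) and S = r × s². The posterior mean variance is (S + 1)/(r - 1) under the identity prior. Under the SAP's vague IGamma(0.001, 0.001) it is about S/(r - 2). Interval width scales with the square root of the ratio. Correlations are multiplied by S/(S + 1) when variances are equal.

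| s² used | S | Identity | Vague | Ratio | Width | Correlation × |
|---|---|---|---|---|---|---|
| Min, mean 0.233 | 8.62 | 0.267 | 0.246 | 1.09 | 1.04 | 0.90 |
| Min, weighted 0.188 | 6.97 | 0.221 | 0.199 | 1.11 | 1.05 | 0.87 |
| WM, mean 0.164 | 6.07 | 0.197 | 0.174 | 1.13 | 1.06 | 0.86 |
| WM, weighted 0.130 | 4.81 | 0.161 | 0.137 | 1.17 | 1.08 | 0.83 |
| WM, lowest 0.0219 | 0.81 | 0.0503 | 0.0232 | 2.17 | 1.47 | 0.45 |

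Over all eight studies, widening is 2-15% (Min) and 3-47% (WM). In a simulation with an assumed within-subject correlation of 0.6, nominal 70% intervals covered 71% (Min, mean variance), 73% (WM, mean) and 87% (WM, lowest). The chance of passing the 0.7 threshold fell by 1-4 points.

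**4. Interim, if the same default applies.** With separate matrices and 14 per arm, r = 13:
- Min: 0.336/0.275 = 1.22 (mean) and 0.287/0.222 = 1.29 (weighted).
- WM: 0.261/0.194 = 1.35 (mean), 0.224/0.154 = 1.46 (weighted) and 0.107/0.0259 = 4.1 (lowest).
- An assumed WM-Min correlation of 0.9 becomes 0.9 × √(0.752 × 0.681) = 0.64 at mean variances, and 0.9 × √(0.710 × 0.628) = 0.60 at weighted ones.

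**5. Predicted success.** SAP Section 3.1 counts success on either endpoint. An approximate simulation used 14 observed and 6 future subjects per arm, zero observed effect and correlation 0.9. Each single endpoint fell from about 25% to 22-24%, but either-endpoint success rose from about 31% to 34-35%. At the smallest variances it was about 31% under both priors. Averaged over simulated interim datasets, the absolute shift was about 2-4 points (90th percentile 5-8), upward on average by 1.5-2.6 points.

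**6. With the fallback.** With scale s², the posterior mean is s²(r + 1)/(r - 1). Relative to s²r/(r - 2) this is (38/36)/(37/35) = 0.999 at the final analysis and (14/12)/(13/11) = 0.99 at interim. Correlation multipliers are 37/38 = 0.97 and 13/14 = 0.93. A wrong guess does little harm at the final analysis. With scale 0.13 and a true WM variance of 0.0219, (0.811 + 0.13)/36 = 0.0261 against 0.0232, a ratio of 1.13 instead of 2.17.

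**The case against.** The strongest reply is that little depends on this. The primary FUV1 model is univariate, with a default residual prior of IGamma(0.001, 0.001). The LAR repeated-measures analysis is exploratory, and the interim prediction belongs to a rule the SAP calls non-binding. At the variances that best reproduce the planned 78% and 81%, final intervals are only 4-6% wider, in the cautious direction. All of that stands.

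The SAP also has safeguards. Section 11.11.1 presents its points as guidance and recommends visualising priors, and its trigger for replacing the identity is not confined to convergence. Section 8.1.2 asks for investigation if the FUV1 results of the two models disagree. These are fair, so a distorted variance is a risk and not a certainty. But they are discretionary, and the stated default fails the SAP's own test of non-informativeness.

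Use of the identity at interim is an inference. Step 1 gives neither df nor scale, asks for non-informative priors suited to each parameter, and the 11.11.1 default is worded for repeated measures. This limits the interim figures to a conditional statement; it also shows that the specification is incomplete.

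A reader might infer that the interim variance is inflated 1.5 to 1.7 times because 0.289 and 0.224 exceed 0.19 and 0.13 by that much. Part of that is ordinary small-sample skew: a vague prior alone gives 13/11 = 1.18 times the sample value. Like for like, the prior accounts for about 1.2-1.5.

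**Conclusion.** The point holds at modest size. The prior is mislabelled for litre-scale endpoints. At typical historical variances it inflates the LAR repeated-measures variance by about 9-11% (Min) and 13-17% (WM), widens intervals by about 4-8%, and weakens correlations. At interim the effect would be larger if the same default is used.

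Three stronger readings are not supported:
- **That the prior swamps the data.** In the final model it supplies more than half of the total sum of squares in only one of the eight WM studies (1/1.81 = 55%); elsewhere, for either endpoint, it supplies 6-27%.
- **That it biases the interim towards futility.** Single-endpoint predictions fall, but under the either-endpoint rule the shift is a few points and upward at zero observed effect with typical variances.
- **That all evidence on durability rests on this model.** SAP Table 15 has LAR responder criteria at FUV2 and FUV3, and efficacy Table 2.1 summarises LAR by visit.

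Assumptions: this study's variances lie in the Table 2 range, centre effects are ignored, and the correlations of 0.6 (between visits) and 0.9 (WM with Min) are not in the documents. For WM-Min, assumed values of 0.8 and 0.95 shrink to 0.57 and 0.68 at mean variances.

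**What to change.** - **LAR models:** in SAP Section 11.11.1, make the existing fallback the default: a diagonal scale matrix of best-guess residual variances from protocol Table 2, about 0.19-0.23 for Min and 0.13-0.16 for WM.
- **EAR models:** Table 2 holds no EAR data, so use residual estimates from simple models, as 11.11.1 already allows.
- **Interim Step 1 (Section 3.1):** state the degrees of freedom and scale matrix, for separate and for pooled matrices.
- **Label:** stop calling the identity scale non-informative for endpoints in litres. It can stay for log2 biomarkers with variances near 1.

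The cost is a few lines in two SAP sections, plus simple EAR fits to obtain the scale. No extra data are needed, and the planned models are otherwise unchanged.
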